### 9.2. Trial Drug Packaging and Labeling

The ELI-002 study product will be provided in two separate kits comprised of 10 vials of Amph-CpG-7909 and 10 vials of Amph-Peptides respectively. In addition, kits containing 10 vials of 10X PBS will be provided to sites. Each vial is for single use only and is labeled according to local regulatory requirements. ELI-002 is for subcutaneous injection.

### 9.3. Trial Drug Storage

**The Amph-Peptides** will contain a mixture of 2 KRAS Amph-Peptide drug substances. The Amph-Peptides are provided as a clear, colorless to slightly yellow, sterile frozen liquid. The recommended storage condition is -20°C. For further details please refer to the Product Manual.

**The Amph-CpG-7909** drug product will be a clear, colorless, sterile liquid fill for injection and the adjuvant will be produced by admixing with the Amph-Peptides drug product. The intended storage condition is -20°C. For further details please refer to the Product Manual.

### 9.4. Trial Drug Preparation

For details and instructions on preparation of the study drug, please see the ELI-002-001 Product Manual.

## 9.5. Administration and Dosage

Subjects will receive SC injections of ELI-002 during the Immunization Period at Visit 3 through Visit 8 (Table 12). Three months after the Immunization Period, subjects will receive SC injections of ELI-002 during the Booster Period at Visit 12 through Visit 15 (see Section 6.1.4, Table 14).

The doses evaluated in the cohorts are as shown in Table 23. All cohorts will enroll RAS mutated PDAC, CRC, NSCLC and OST (including ovarian, bile duct and gallbladder carcinoma).

**Table 23: Phase 1 Cohorts and Doses**

	Cohort	Tumor	Dose Level
Dose Escalation	Cohort 1	KRAS/NRAS mutated solid tumors	Amph-CpG-7909 0.1 mg with Amph-Peptides
	Cohort 2	KRAS/NRAS mutated solid tumors	Amph-CpG-7909 0.5 mg with Amph-Peptides
	Cohort 3	KRAS/NRAS mutated solid tumors	Amph-CpG-7909 2.5 mg with Amph-Peptides

KRAS=Kirsten rat sarcoma; NRAS=neuroblastoma ras viral oncogene homolog; OST=other solid tumors

## 9.6. Trial Drug Accountability

The investigator is responsible for trial drug accountability, reconciliation, and record maintenance. Drug accountability records will be maintained during the trial, including the amount of trial drug received from the Sponsor (or Sponsor's designee), the amount distributed to each subject, and the amount of unused drug destroyed at the site or returned to the Sponsor for destruction.

The trial center will maintain a log of all trial drug prepared and administered to subjects, as well as destruction of used/unused vials. Administration of the drug product admix (the test article) will occur during the Immunization Period and the Booster Period, according to the Schedule of Assessments (Table 12 and Table 14).

Trial center personnel should refer to the Product Manual for instructions regarding disposal of any trial drug or used trial drug packaging.

## 9.7. Trial Drug Handling and Disposal

All used and unused trial drug supplies must remain stored at the clinical site in a secure location and within appropriate temperature conditions up until receiving instructions for destruction. Disposal of trial drug will be conducted in compliance with all applicable laws and regulations.

## 10. TIMING OF TRIAL PROCEDURES

Home Health Visits: Based on assessment of risk, and to ensure subject safety and minimize risks to trial integrity, off-site study visits can be performed in the event a study participant cannot attend an on-site visit during the COVID-19 crisis [[Food and Drug Guidance, 2020](#)]. The procedures that cannot be performed during a home health visit include:

- CT/MRI scans
- First ELI-002 dose administration (Visit 3, Day 57); this must occur on-site as per Section [10.2](#).
- Leukapheresis (Visit 2, Visit 9)

The informed consent form will describe the availability of home health visits if applicable at the clinical site.

The subject will be invited to continue future study visits on-site per protocol, as soon as local and federal Covid-19 regulations allow.

### 10.1. Screening and Observation Period

**Visit 1 (Day 10)**, subjects will provide written informed consent before any trial-related procedures are performed.

- Once a subject has consented among the first procedures will be:
  - A retrospective tumor tissue sample from the prior surgery will be requisitioned for WES. Tumor DNA will be sequenced to guide ctDNA testing in subsequent blood samples and baseline tumor gene expression will be assessed ([Table 11](#)).
  - In parallel, a 6-mL ethylenediaminetetraacetic acid (EDTA) whole blood tube will be collected and shipped at the same time as the tissue sample. The somatic DNA from the EDTA tube will serve as a control to ensure only tumor-specific DNA is included for subsequent ctDNA testing.

**At Visit 2 (Day 26 ±5 days)**, the following visit procedures will include:

- Administer the EORTC QLQ-C30 and the tumor type-specific PRO (see [Section 11.3](#)).
- Collect a urine sample for a pregnancy test for women of childbearing potential.
- Record demographic information (including sex, age, race and ethnicity).
- Record height and weight.
- Record medical and medication history, including cancer history/prior treatments and current medications.
- Review available eligibility criteria. While mKRAS/mNRAS and ctDNA results may not yet be available, the expectation is that these will be reviewed, and full eligibility determined, prior to Visit 3.

- Perform a physical examination which will be based on institution standard of care(see [Section 12.1.3](#)).
- Record vital signs (blood pressure, pulse rate, body temperature, and respiratory rate). Measurements will be obtained after 3 minutes in the sitting position. No other measurements or procedures should be performed during this 3-minute period.
- Perform a 12-lead ECG (to be reviewed by a cardiologist or clinical investigator according to institutional guidelines and practice).
- Perform an ECOG Scale of Performance Status. To be eligible, ECOG performance status must be 0 to 1.
- Perform a CT with contrast within 90 days of first ELI-002 dose, following resection or after last administration of adjuvant treatment, whichever is last in the specific subject treatment plan. For subjects with IV contrast allergy/intolerance, MRI may be performed. The same modality should be used for all imaging throughout the trial.
- Collect a blood sample for clinical laboratory assessments, including the cytokine panel (local laboratory; see [Section 11.1](#) and [Section 12.1.6](#)).
- Collect a sample appropriate for the available test method for active Covid-19 infection (local laboratory).
- Collect a blood sample for ctDNA test  $\geq 21$  days post-surgery or after last administration of adjuvant treatment, whichever is last in the specific subject treatment plan (to be performed at a central laboratory).
- Collect blood sample(s) (local laboratory, see Inclusion Criteria #4 in Section 7.1). Biomarker values must be obtained  $\geq 21$  days post-surgery or after the last administration of adjuvant therapy, whichever comes last in the specific subject's treatment plan.
- Collect a leukapheresis for immunogenicity assessment (central laboratory). The leukapheresis must be collected once eligibility has been confirmed and prior to the first dose of ELI-002.
- Record any pre-treatment SAEs that have occurred.

#### 10.1.1. Rescreening

Subjects are allowed to rescreen for the ELI-002-001 trial. No screening procedures, other than what may need to be repeated due to screen failure, will need to be repeated as long as the screening CT/MRI scan was performed  $\leq 90$  days from the time of the anticipated first dose of trial drug. If the CT/MRI scan was performed  $>90$  days from the anticipated first dose, then it will need to be repeated and reviewed, to ensure that the patient is negative for recurrent disease, per the protocol inclusion criteria.

Other screening evaluations can be repeated as deemed appropriate and necessary by the investigator.

## 10.2. Immunization Period

During the Immunization Period, subjects will receive 4 weekly SC injections (Weeks 1 to 4) followed by 2 injections at Week 6 and Week 8 (Table 12). If the subject has fever  $\geq 38.0^{\circ}\text{C}$  and/or elevated IL-6  $\geq 500$  pg/mL, proceed with the visit but omit study treatment administration; if fever abates and cytokines diminish to  $< 500$  pg/mL, the subject may proceed with the next scheduled dose after approval from the medical monitor). In addition, if a subject exhibits IFN $\gamma$   $\geq 1000$  pg/mL, the Elicio medical monitor should be contacted for consultation.

All laboratory samples should be taken prior to dosing on any study visit that has dosing.

At **Visit 3 (Baseline, Day 57) prior to trial drug administration**, the following visit procedures will include:

- Administer the EORTC QLQ-C30 and the tumor type-specific PRO (see Section 11.3).
- Record any change in medical history since the previous visit. Subjects must have recovered from surgery without any ongoing medical/surgical issues.
- Record any change in cancer history since the previous visit.
- Perform a physical examination which will be based on institution standard of care (see Section 12.1.3). In addition, a neurological examination for baseline assessment of ICANS/ICE will be performed.
- Record vital signs (blood pressure, pulse rate, body temperature, and respiratory rate).
- Record weight.
- Perform a 12-lead ECG (to be reviewed by a cardiologist or clinical investigator according to institutional guidelines and practice).
- Confirm ECOG Scale of Performance Status is 0 or 1.
- Record any change in concomitant medications since the previous visit.
- Collect a blood sample for clinical laboratory assessments, including the cytokine panel (local laboratory; see Section 11.1 and Section 12.1.6). Note: cytokine testing should be performed within 7 days prior to dosing.
- Collect a blood sample for ctDNA (to be performed at a central laboratory).
- Collect a blood sample for high resolution HLA typing (central laboratory).
- Record any pre-treatment SAEs that have occurred since the previous visit.

**Dose 1:** The first dose must be administered at the clinical site. Subjects must be observed by study staff for at least 1-hour postdose for observation and must stay within an hour of the clinic for  $\geq 24$  hours in order to monitor for potential AEs such as CRS.

**After dose administration** the following visit procedures will occur:

- Record vital signs (blood pressure, pulse rate, body temperature, and respiratory rate). Measurements will be obtained after 3 minutes in the sitting position. No other measurements or procedures were performed during this 3-minute period.
- Subjects will be provided with the reactogenicity diary to complete for 7-days following the dose. Subjects will be instructed how to complete the diary and to return the completed form at their next visit.

At **Visit 4 (Day 64)**, the following visit procedures will include:

- Administer the EORTC QLQ-C30 and the tumor type-specific PRO (see [Section 11.3](#)).
- Perform a physical examination, which will be based on institution standard of care (see [Section 12.1.3](#)).
- Record vital signs (blood pressure, pulse rate, body temperature, and respiratory rate). Measurements will be obtained after 3 minutes in the sitting position. No other measurements or procedures were performed during this 3-minute period.
- Record weight.
- Confirm ECOG Scale of Performance Status.
- Record any change in concomitant medications since the previous visit.
- All laboratory samples should be taken prior to dosing on any study visit that has dosing.
  - Collect a blood sample for clinical laboratory assessments, including the cytokine panel (local laboratory; see [Section 11.1](#) and [Section 12.1.6](#)). Note: cytokine testing should be performed and reviewed within 7 days prior to dosing.
- Record any AEs since last visit. Check for signs of toxicity. Including fever, and laboratory evidence of elevated cytokines. Hold the ELI-002 dose if Grade  $\geq 2$  CRS is present, or if elevated cytokine IL-6 is present. If elevated IFN $\gamma$  is present, the Elicio medical monitor should be contacted for consultation([Section 6.8.1](#)).
- **Dose 2:** Trial drug administration and subjects must be observed by study staff for at least 1-hour postdose for observation.
- Subjects will be provided with the reactogenicity diary to complete for 7-days following the dose. Subjects will be instructed how to complete the diary and to return the completed form at their next visit.

At **Visit 5 (Day 71)**, the following visit procedures will include:

- Administer the EORTC QLQ-C30 and the tumor type-specific PRO (see [Section 11.3](#)).
- Perform a physical examination, which will be based on institution standard of care (see [Section 12.1.3](#)).

- Record vital signs (blood pressure, pulse rate, body temperature, and respiratory rate). Measurements will be obtained after 3 minutes in the sitting position. No other measurements or procedures were performed during this 3-minute period.
- Record weight.
- Confirm ECOG Scale of Performance Status.
- Record any change in concomitant medications since the previous visit.
- All laboratory samples should be taken prior to dosing on any study visit that has dosing.
  - Collect a blood sample for clinical laboratory assessments, including the cytokine panel (local laboratory; see Section 11.1 and Section 12.1.6). Note: cytokine testing should be performed and reviewed within 7 days prior to dosing.
  - Collect a whole blood sample for immunogenicity testing (central laboratory).
- Record any AEs since last visit. Check for signs of toxicity, including fever and laboratory evidence of elevated cytokines. Hold the ELI-002 dose if Grade  $\geq 2$  CRS is present, or if elevated cytokine IL-6 is present. If elevated IFN $\gamma$  is present, the Elicio medical monitor should be contacted for consultation (Section 6.8.1).
- **Dose 3:** Trial drug administration and subjects must be observed for safety for at least 1-hour postdose.
- Subjects will be provided with the reactogenicity diary to complete for 7-days following the dose. Subjects will be instructed how to complete the diary and to return the completed form at their next visit.

At **Visit 6 (Day 78)**, the following visit procedures will include:

- Administer the EORTC QLQ-C30 and the tumor type-specific PRO (see Section 11.3).
- Perform a physical examination, which will be based on institution standard of care (see Section 12.1.3).
- Record vital signs (blood pressure, pulse rate, body temperature, and respiratory rate). Measurements will be obtained after 3 minutes in the sitting position. No other measurements or procedures were performed during this 3-minute period.
- Record weight.
- Confirm ECOG Scale of Performance Status.
- Record any change in concomitant medications since the previous visit.
- All laboratory samples should be taken prior to dosing on any study visit that has dosing.
  - Collect a blood sample for clinical laboratory assessments, including the cytokine panel (local laboratory; see Section 11.1 and Section 12.1.6). Note: cytokine testing should be performed and reviewed within 7 days prior to dosing.

- Collect a blood sample for ctDNA.
- Record any AEs since last visit. Check for signs of toxicity, including fever and laboratory evidence of elevated cytokines. Hold the ELI-002 dose if Grade  $\geq 2$  CRS is present, or if elevated cytokine IL-6 is present. If elevated IFN $\gamma$  is present, the Elicio medical monitor should be contacted for consultation ([Section 6.8.1](#)).
- **Dose 4:** Trial drug administration and subjects must be observed for safety for at least 1-hour postdose.
- Subjects will be provided with the reactogenicity diary to complete for 7-days following the dose. Subjects will be instructed how to complete the diary and to return the completed form at their next visit.

At **Visit 7 (Day 92)**, the following visit procedures will include:

- Administer the EORTC QLQ-C30 and the tumor type-specific PRO (see [Section 11.3](#)).
- Perform a physical examination, which will be based on institution standard of care (see [Section 12.1.3](#)).
- Record vital signs (blood pressure, pulse rate, body temperature, and respiratory rate). Measurements will be obtained after 3 minutes in the sitting position. No other measurements or procedures were performed during this 3-minute period.
- Record weight.
- Confirm ECOG Scale of Performance Status.
- Record any change in concomitant medications since the previous visit.
- All laboratory samples should be taken prior to dosing on any study visit that has dosing.
  - Collect a blood sample for clinical laboratory assessments, including the cytokine panel (local laboratory; see [Section 11.1](#) and [Section 12.1.6](#)). Note: cytokine testing should be performed and reviewed within 7 days prior to dosing.
  - Collect a whole blood sample for immunogenicity testing (central laboratory).
- Record any AEs since last visit. Check for signs of toxicity, including fever and laboratory evidence of elevated cytokines. Hold the ELI-002 dose if Grade  $\geq 2$  CRS is present, or if elevated cytokine IL-6 is present. If elevated IFN $\gamma$  is present, the Elicio medical monitor should be contacted for consultation ([Section 6.8.1](#)).
- **Dose 5:** Trial drug administration and subjects must be observed for safety for at least 1-hour post dose.
- Subjects will be provided with the reactogenicity diary to complete for 7-days following the dose. Subjects will be instructed how to complete the diary and to return the completed form at their next visit.

At **Visit 8 (Day 106)**, the following visit procedures will include:

- Administer the EORTC QLQ-C30 and the tumor type-specific PRO (see [Section 11.3](#)).
- Perform a physical examination, which will be based on institution standard of care (see [Section 12.1.3](#)).
- Record vital signs (blood pressure, pulse rate, body temperature, and respiratory rate). Measurements will be obtained after 3 minutes in the sitting position. No other measurements or procedures were performed during this 3-minute period.
- Record weight.
- Confirm ECOG Scale of Performance Status.
- Record any change in concomitant medications since the previous visit.
- All laboratory samples should be taken prior to dosing on any study visit that has dosing.
  - Collect a blood sample for clinical laboratory assessments, including the cytokine panel (local laboratory; see [Section 11.1](#) and [Section 12.1.6](#)). Note: cytokine testing should be performed and reviewed within 7 days prior to dosing.
- Record any AEs since last visit. Check for signs of toxicity, including fever and laboratory evidence of elevated cytokines. Hold the ELI-002 dose if Grade  $\geq 2$  CRS is present, or if elevated cytokine IL-6 is present. If elevated IFN $\gamma$  is present, the Elicio medical monitor should be contacted for consultation ([Section 6.8.1](#)).
- **Dose 6:** Trial drug administration and subjects must be observed for safety for at least 1-hour postdose.
- Subjects will be provided with the reactogenicity diary to complete for 7-days following the dose. Subjects will be instructed how to complete the diary and to return the completed form at their next visit.

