## **6.7. Management of Study Drug-Related Events**

### **6.7.1. Temporarily Suspending Treatment Administration**

If a subject meets any of the following conditions within 48 hours prior to the scheduled administration of the trial treatment, treatment administration will be temporarily suspended:

1. To reduce the risk of CRS, subjects will not be given a repeat dose of ELI-002 if they are exhibiting  $T \geq 38^{\circ}\text{C}$  and/or  $\text{IL-6} \geq 500 \text{ pg/mL}$  (cytokine collection, including IL-6, may be performed up to 7 days prior to treatment). In addition, if a subject exhibits  $\text{IFN}\gamma \geq 1000 \text{ pg/mL}$ , the Elicio medical monitor should be contacted for consultation.
2. Adverse event(s) that meet the definition of DLT caused by prior treatment. See [Section 6.7.3](#) for the definition of a DLT; see [Section 12.4](#) for the definition of Common Terminology Criteria for Adverse Events (CTCAEs).
3. Any subsequent dosing in a subject who has experienced Grade  $\geq 2$  CRS/ immune effector cell-associated neurotoxicity syndrome (ICANS)

Investigators must consult the medical monitor to discuss any subjects meeting the above criteria.

In the event the ELI-002 dose is held, the subject should not receive any make up dose and remain on the original protocol schedule (ie, their next dose will be at the next protocol-specified dose if they meet the criteria for dosing). All trial procedures and treatment administration will be resumed as soon as the subject's condition allows or at the investigator's discretion after Sponsor approval.

The trial may proceed at a lower dose, at a less frequent schedule, or omitting the Amph-CpG-7909 adjuvant while continuing to administer the Amph-Peptides, based on emerging toxicity or pharmacodynamic data until the MTD is determined.

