### 6.8.1. Management of Cytokine Release Syndrome

Since ELI-002 activates T cells by a novel amphiphile mechanism whereby potent responses are generated, there is a theoretical risk for observation of T-cell-mediated toxicity.

To reduce the risk of CRS, subjects will not be given a repeat dose of ELI-002 if they are exhibiting  $T > 38^{\circ}\text{C}$  and/or  $\text{IL-6} > 500 \text{ pg/mL}$ . In addition, if a subject exhibits  $\text{IFN}\gamma \geq 1000 \text{ pg/mL}$ , the Elicio medical monitor should be contacted for consultation.

In the event the ELI-002 dose is held, the subject should not receive any make up dose and remain on the original protocol schedule (ie, their next dose will be at the next protocol-specified dose if they meet the criteria for dosing and with approval from the medical monitor).

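### The dose-hold sentence at the repeat-dose visits omits ICANS and does not cite Section 6.7.1, whose 48-hour lead-in leaves resolved CRS unclear

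*Protocol*

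**What the plan says.** Two parts of the protocol tell a site when to withhold a repeat dose.

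**Section 6.7.1 (temporary suspension).** The lead-in applies to a subject who meets a listed condition "within 48 hours prior to the scheduled administration of the trial treatment, treatment administration will be temporarily suspended". Three conditions follow:

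1. Fever and/or high IL-6, with the allowance that "cytokine collection, including IL-6, may be performed up to 7 days prior to treatment".
2. "Adverse event(s) that meet the definition of DLT caused by prior treatment".
3. "Any subsequent dosing in a subject who has experienced Grade" 2 or higher CRS or ICANS.

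The section then adds: "Investigators must consult the medical monitor to discuss any subjects meeting the above criteria".

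**Sections 10.2 and 10.4 (visit instructions).** At Visits 4-8 and 12-15 the site is told to hold the dose if Grade 2 or higher "CRS is present, or if elevated cytokine IL-6 is present", and to contact the medical monitor if IFN-gamma is elevated. Each of these sentences cites Section 6.8.1. The introductions to 10.2 and 10.4 add an omission rule for fever and IL-6 only.

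**Section 6.8.1, the section cited.** Its rule is that "subjects will not be given a repeat dose of ELI-002 if they are exhibiting" a raised temperature and/or raised IL-6. It has no criterion based on CRS grade or on ICANS.

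**The concern.** A coordinator or investigator deciding on a dose at the visit is likely to work from the visit instructions. Those instructions differ from 6.7.1 in two ways. They look at the subject's current state, whereas condition 3 is worded in terms of what the subject has had. They also name CRS alone, whereas condition 3 names CRS and ICANS. The cross-reference does not repair this, because it leads to 6.8.1 and not to 6.7.1.

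Section 6.8 itself recognises that CRS and ICANS can be serious or fatal, and this is a first-in-human trial. The suspension is temporary, so a recovered subject may properly be dosed again. What could be lost is the pause and the required conversation with the medical monitor before the next dose.

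**Working it through.** No sample size, error rate or event count is involved. The check compares the texts, with a little arithmetic on the visit calendar.

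**1. How many visits carry the narrower sentence.** In Section 10.2 it appears at Visits 4, 5, 6, 7 and 8 (Doses 2-6). In Section 10.4 it appears at Visits 12, 13, 14 and 15 (Doses 7-10). That is 5 + 4 = 9, which is every repeat dose. Section 6.1.2 requires medical monitor agreement before boosters resume after toxicity and cites 6.7.1, so it covers Doses 7-10. That leaves 9 - 4 = 5 doses, Doses 2-6, with no equivalent sentence.

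**2. The rules side by side.**

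| Subject's state before a repeat dose | Visit sentence | Section 6.8.1 | Section 6.7.1 |
|---|---|---|---|
| Grade 2 or higher CRS, ongoing | Hold | Only if temperature or IL-6 is raised | Hold and consult |
| Grade 2 or higher ICANS, ongoing | Not named | No trigger | Hold and consult |
| Grade 2 or higher CRS or ICANS, resolved more than 48 hours ago | Not named | No trigger | Hold and consult on the wording of condition 3; outside the rule if the lead-in is applied to the event |
| DLT more than 48 hours old | Not named | No trigger | Hold and consult under condition 2; outside the rule if the lead-in is applied to the event |

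The ICANS row does not depend on how the lead-in is read.

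**3. Whether another rule catches Grade 2 ICANS.** The severity-based DLT criteria in 6.7.3 start at Grade 3, so a Grade 2 event does not reach condition 2. Section 6.8.3 covers evaluation and treatment of ICANS and has no dose hold. Section 6.7.2 does not name it. Condition 3 of 6.7.1 is the only dosing criterion that does.

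**4. What the 48-hour lead-in does.** On nominal days, Dose 1 is on Day 57 and Dose 2 on Day 64. Take Grade 2 CRS on days 1-4 after Dose 1, that is, Days 58-61. The window opens on Day 64 - 2 = Day 62, after the event has ended. If the window must contain the event, this subject is outside 6.7.1. If condition 3 refers to history, the subject is inside it.

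The literal reading would exclude most of the time between doses:

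- Weekly interval: 7 x 24 = 168 hours; 168 - 48 = 120 hours outside the window (120/168 = 71%).
- Two-week interval (Doses 4 to 5 and 5 to 6): 14 x 24 = 336 hours; 336 - 48 = 288 hours outside (288/336 = 86%).

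These are shares of elapsed time, not probabilities of an event. They show that the literal reading would largely empty a condition worded as history. It would also let a DLT that ended early in the interval go without suspension.

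**The case against.** The best reply is that the instructions are cumulative. The visit sentence says when to hold. It does not say that these are the only reasons, and it does not permit a dose that 6.7.1 suspends. Several other provisions also point the right way:

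- Table 12 footnote 8 and Table 14 footnote 7 send the site to Section 6.7 at every dosing visit. Section 6.1.1 refers to 6.7, and 6.7.3 refers to 6.7.1.
- Section 6.8.1 requires medical monitor approval for the next dose after any held dose, so ongoing CRS held under the visit text still reaches the monitor.
- CRS and ICANS follow SAE timelines (12.2.1.2), which means 1 business day from awareness (12.7). The medical monitor reviews safety continuously (6.6).

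All of this stands, and it lowers the risk. It does not put the hold in the visit instruction. The footnotes point to 6.7 as a whole, while the dosing bullet itself points elsewhere. Reporting is not a hold: a site that first hears of an event while recording adverse events at the visit could dose that day and still report on time.

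Three stronger readings are tempting, and the documents do not support them:

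- A reader might infer that the visit text authorises dosing after ICANS. It is silent; it grants no permission.
- A reader might infer that 6.7.1 plainly suspends Dose 2 in the Day 58-61 example. That rests on one reading of a lead-in that can be read two ways.
- A reader might infer that nothing at the visit would bring ICANS to mind. The formal ICANS/ICE examination is specified only at Visit 3. But Table 17, inside the cited 6.8.1, lists confusion, aphasia and seizures among the warning signs, and each of these visits includes a physical examination and adverse event recording.

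**Conclusion.** The mismatch is real and worth correcting. The omission of Grade 2 or higher ICANS, and the failure to cite 6.7.1, are firm under any reading. The omission of resolved Grade 2 or higher CRS is a discrepancy if condition 3 is read as history. Its wording favours that reading, but the lead-in leaves room for doubt, and that doubt is itself a defect in 6.7.1.

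All nine repeat-dose visits carry the sentence; the practical exposure is mainly Doses 2-6. The number of subjects affected cannot be stated because neither document gives an expected CRS or ICANS rate. The conclusion assumes that some sites will dose from the visit text without following the schedule footnote to 6.7. The documents do not show how often that would happen. What is at stake is the hold and the consultation, not a permanent bar on dosing.

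**What to change.** **Visit text (Visits 4-8 and 12-15).** Replace each hold sentence with an instruction to hold the dose and consult the medical monitor if any 6.7.1 criterion is met. State that this includes any Grade 2 or higher CRS or ICANS, ongoing or resolved, that the medical monitor has not already cleared. Cite 6.7.1.

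**Section 6.7.1.** Apply the 48-hour window to condition 1 only, keeping the 7-day allowance for cytokine collection. State that conditions 2 and 3 apply until the medical monitor clears re-dosing.

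**Cost.** No new visit, sample or assessment is needed. The hold rule in 6.7.1 changes in substance, so this needs a protocol amendment with IRB review; a site memo alone is not enough. The clearance clause is new to the protocol; it prevents one reviewed event from holding every later dose. Some doses will be lost, because after a hold "the subject should not receive any make up dose and remain on the original protocol schedule". The SAP (Table 8) measures dose intensity against a full course of ten vaccinations, so each lost dose lowers a subject's value by at most 1/10.
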